**Please DO NOT access the patient's record prior to completing this form!**

Did the patient have any of the following before transfer to the postpartum floor?

	YES	NO
Nausea?		
Vomiting?		
Diarrhea?		
Shortness of Breath?		
Headache?		
Blurred Vision?		
Severe Anxiety?		
Chest Pain?		
Abnormal Sweating?		

Patient Name: \_\_\_\_\_

MRN: \_\_\_\_\_

Study Number: \_\_\_\_\_

Date/Time of Interview: \_\_\_\_\_

Questions or Concerns:

[name]  
e: [contact]  
pg: [name]

Page 63 of 99

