### Attachments

Name	Mode
8.17.2021 Consent Form - CLEAN	Electronic
04.19.22 Methergine Hemabate IRB Detailed Protocol--CLEAN (Detailed Protocol)	Electronic
Second-Line Uterotonics- Data Collection Sheet (Data Collection Form)	Electronic
Uterine Tone Score Intraop Data Collection_4.29.19 (Data Collection Form)	Electronic
8.17.2021 Flier- CLEAN (Flyer)	Electronic
8.17.2021 18-24 Hour Interview Guide- CLEAN (Instrument/Questionnaire)	Electronic
8.17.2021 2-4 Hour Interview Guide - CLEAN (Instrument/Questionnaire)	Electronic
Continuing Review Adverse Event Attestation (Other)	Electronic
Correspondence_for_STU00214439 (Other)	Electronic
Methergine Package Insert (Package Insert)	Electronic

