## II. **SPECIFIC AIMS** (Research Objectives)

We hypothesize that the administration of methergonovine will be associated with a 1 point greater reduction in uterine tone (on a 0-10 scale) at 10 minutes after administration compared to carboprost.

1. The primary outcome will be the uterine tone score on a 0 to 10 scale 10 minutes after administering the study drug. A score of 0 will mean the uterus has 'no tone'. A score of 10 will mean there is 'excellent tone'.
2. Secondary outcomes will include:
  - a) change in uterine tone from the time of study drug administration to 5 minutes later,
  - b) administration of an additional uterotonic agent after the first study drug
  - c) number of transfused blood products within 24 hours from the time of delivery,
  - d) any surgical intervention intended to control bleeding: i.e. Bakri balloon, O'Leary stitch, d&e, exploratory laparotomy, B-Lynch sutures, hysterectomy or interventional radiology artery embolization,
  - e) intraoperative quantitatively measured blood loss (QBL),
  - f) pre-delivery to postpartum change in serum hemoglobin,
  - g) vasopressor requirement or hypovolemic shock
  - h) postpartum admission to the intensive care unit (ICU),
  - i) need for postoperative mechanical ventilation,
  - j) nausea, vomiting, or diarrhea, abdominal pain, shortness of breath, headache, blurred vision, anxiety, chest pain, sweating, or palpitations within 2 hours postpartum
  - k) hypertensive emergency (SBP>/=160 or DBP>/=110)
  - l) EKG changes indicative of myocardial ischemia,
  - m) acute renal dysfunction,
  - n) length of postoperative hospital stay,
  - o) postpartum acute lung injury or circulatory fluid overload in the context of blood product transfusion,
  - p) allergic reaction deemed the result of blood product transfusion

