Within the first 24 hours after delivery, but no sooner than the time of patient transfer from the labor and delivery floor to the postpartum unit, Between 2-4 hours postpartum and again between 18-24 hours postpartum, a blinded study investigator who is not involved in the subject's clinical care will interview the patient by phone (to avoid physical contact and minimize the risk for COVID-10 transmission) and record the information from the interview on the corresponding '2-4 Hr Interview Guide' or '18-24 Hr Interview Guide'. This will allow them to assess subjective side effects of the study medication such as G.I. upset, dizziness, shortness of breath, palpitations or chest pain. Non-English speaking patients will be interviewed in person with the assistance of an in-person interpreter from BWH Interpreter Services.

Subject randomization, patient MRN and the linked study ID number will be documented on a separate form in the secure electronic database, REDCap database by the unblinded principal investigator. This form will be visible only to the principal investigator. An unblinded study investigator (i.e. the principal investigator, or a research assistant, when one is hired in the future) with access to REDCap will be responsible for collecting and entering all primary and secondary outcomes from the Uterine Tone Score Intraop Data Collection sheet, the 2-4 Hour Interview Guide and the 18-24 Hour Interview Guide and Epic medical records (including side-effects of study medications) into REDCap. Subject randomization will be documented, on a separate form in the database to which only the principal investigator has access, in order to preserve the integrity of the data collection and entry.

The need for blood product administration and quantity of each component given within 24hrs after cesarean section will be recorded. In addition, the investigator will record any additional interventions performed to halt bleeding, such as Bakri balloon placement, B-Lynch sutures, uterine artery embolization or hysterectomy.

Total intravenous fluids given from start to conclusion of the delivery will be recorded. The use of vasopressors, uterotonic agents, anti-emetic agents will be recorded. Length of stay and any postoperative complications occurring during the hospital stay will be documented at the time of hospital discharge.

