**Please DO NOT access the patient's record prior to completing this form!**

Did the patient have any of the following before transfer to the postpartum floor?

	YES	NO
Nausea?		
Vomiting?		
Diarrhea?		
Shortness of Breath?		
Headache?		
Blurred Vision?		
Severe Anxiety?		
Chest Pain?		
Abnormal Sweating?		

Patient Name: \_\_\_\_\_

MRN: \_\_\_\_\_

Study Number: \_\_\_\_\_

Date/Time of Interview: \_\_\_\_\_

Questions or Concerns:

[name]  
e: [contact]  
pg: [name]

Page 62 of 99

**2-4 HR POSTPARTUM  
BLINDED INTERVIEW GUIDE  
SECOND-LINE UTEROTONICS in PPH STUDY**

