At the end of the C/S, the anesthesiologist will return the Randomization sheet and the Uterine Tone Score Intraop Data Collection sheet in the previously sealed envelope to a folder where all paper documents for the study are temporarily stored in a locked room on the L&D floor. On each day of subject enrollment, the unblinded principal investigator will collect the envelope with the Randomization sheet and Uterine Tone Score Intraop Data Collection sheet and transfer it to a locked filing cabinet in a locked office to which only the principal investigator has access.

After the subject has recovered on the L&D floor and is ready for transfer to the postpartum floor, a blinded study co-investigator will interview the patient by phone (to limit physical contact, due to COVID-19 precautions)

using the '2-4 Hour Interview Guide'. At 18-24 hours postpartum, the subject will again be interviewed by phone by a blinded study co-investigator, using the '18-24 Hour Interview Guide'. Both postpartum interview guides will contain the same content, allowing for subjective adverse effects to be accurately assessed at 2 timepoints. (no later than 24 hours after delivery). This data will be documented on the 2-4 Hour and 18-24 Hour Interview Guides, to be retrieved by the principal investigator (who is not blinded) after the day of subject enrollment, then stored in the locked office, and ultimately entered into a secure electronic database, REDCap, by a blinded study investigator. This will allow them to assess for any subjective side effects of the study medication, as listed below (Secondary Endpoint #9).

An unblinded study investigator not involved in data collection and with access to REDCap will be responsible for collecting all primary and secondary outcomes (including side-effects of study medications) from the Uterine Tone Score Intraop Data Collection sheet, the Pre Transfer Interview Guide and Epic medical records onto the Second Line Uterotonics Data Collection Sheet and entering this information into REDCap. Subject randomization, patient MRN and the linked study ID number will be documented on a separate form in the REDCap database by the unblinded principal investigator, to preserve the integrity of the data collection and entry.

Study endpoints will be:

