#### Secondary Endpoints

1. Uterine tone score recorded at 5 minutes following the administration of the second-line uterotonic.
2. Need for an additional uterotonic agent after the study drug
3. Number of units of blood products transfused ( $t_0$  = time of delivery;  $t_{final}$  = 24 hours after delivery)
4. Need for a surgical or radiologic intervention to control bleeding
5. Quantitative intrapartum blood loss
6. Pre- vs post-delivery hematocrit values
7. Maternal morbidity: vasopressor requirement or hypovolemic shock, admission to the intensive care unit postpartum, mechanical ventilation, hypertensive emergency, myocardial ischemia, acute kidney injury, acute lung injury or circulatory overload from blood transfusion, allergic reaction deemed the result of blood transfusion, hypovolemic shock, or vasopressor requirement.
8. Length of postoperative hospital stay

9. Medication side effects within 2 hrs postpartum: nausea, vomiting or diarrhea, abdominal pain, shortness of breath, headache, blurred vision, anxiety, chest pain, sweating, palpitations

For studies involving treatment or diagnosis, provide information about standard of care at Partners (e.g., BWH, MGH) and indicate how the study procedures differ from standard care. Provide information on available alternative treatments, procedures, or methods of diagnosis.

All patients undergoing a C/S delivery at the Brigham and Women's Hospital (BWH) have a peripheral IV and baseline laboratory work on admission to the labor and delivery floor. The standard of care at BWH for women undergoing C/S includes spinal anesthesia with bupivacaine, fentanyl, and morphine, as will be used in this study unless contraindicated. The overall anesthetic management of a patient in the operating room will be at the discretion of the anesthesia attending physician, including crystalloid fluid administered, anti-emetic medication, analgesic medication and vasopressors used. Blood products transfused will be at the discretion of the attending physicians.

At the time of C/S and clamping of the umbilical cord, a standard infusion of oxytocin 30U/500mL is begun at a rate of 15-30U/hr. If uterine tone is perceived to be inadequate, this rate may be increased and the obstetrician may attempt maneuvers to improve uterine tone. Additionally, at this time a second-line uterotonic is typically requested.

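### Both interview guides lack two of the 11 symptoms in secondary outcome j and ask about the time before transfer, not the first 2 hours

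*Protocol*

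**What the plan says.** The endpoint is stated twice in matching terms. Section II of the Detailed Protocol gives outcome j as "nausea, vomiting, or diarrhea, abdominal pain, shortness of breath, headache, blurred vision, anxiety, chest pain, sweating, or palpitations within 2 hours postpartum". Endpoint 9 of the Protocol Summary reads "Medication side effects within 2 hrs postpartum: nausea, vomiting or diarrhea, abdominal pain, shortness of breath, headache, blurred vision, anxiety, chest pain, sweating, palpitations".

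The collection tool is a telephone interview by a blinded investigator, held twice, at nominal times of 2-4 and 18-24 hours postpartum (Section V, Study Procedures). Both surviving guide forms open with "Did the patient have any of the following before transfer to the postpartum floor" and then list the same nine yes/no items. The Protocol Summary (Research Design and Methods) confirms that the two guides are meant to have the same content.

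Other sections describe a wider enquiry. Section V gives palpitations and dizziness among its examples of what the interview assesses. Section VII (Risks and Discomforts), which names abdominal pain as a methylergonovine reaction, says that all the side effects it lists will be evaluated at transfer and again at 18-24 hours.

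The time of the first call is given in three ways. Section V has 2-4 hours but also "no sooner than the time of patient transfer from the labor and delivery floor to the postpartum unit". The Protocol Summary has "After the subject has recovered on the L&D floor and is ready for transfer to the postpartum floor". Section VII has the time of transfer itself. The Summary also still names "the Pre Transfer Interview Guide and Epic medical records" among its data sources, which would fit a question carried over from a single pre-transfer form.

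**The concern.** An endpoint can be reported only as it was asked. If two listed symptoms have no question, a low count for either may mean that nobody asked, and a reader of the results table could take it as absence. Both are side effects on which the two drugs might be compared. The Methergine label lists abdominal pain and palpitation. The Hemabate label lists palpitations, together with epigastric and dysmenorrhea-like pain.

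The time window raises a separate problem. A symptom reported as occurring before transfer may have begun after the first 2 hours, and the forms give no means of telling. A table headed with the 2-hour window would then describe something that was not measured.

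The second call matters too, because its name suggests a later assessment while its question points back to the early period.

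**Working it through.** No formula in the plan is at issue. The check compares the endpoint's list with the forms.

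**Step 1. Symptoms.** Inputs are outcome j (Section II), the two guides, and the visible symptom columns of the data collection sheet that follows the reference list. That table is broken in extraction, so only its visible columns are used.

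| Outcome j | Both guides | Data sheet (visible) |
|---|---|---|
| nausea | yes | yes |
| vomiting | yes | yes |
| diarrhea | yes | yes |
| abdominal pain | **no row** | **none seen** |
| shortness of breath | yes | yes, as dyspnea |
| headache | yes | yes |
| blurred vision | yes | yes |
| anxiety | only if severe | only if severe |
| chest pain | yes | yes |
| sweating | only if abnormal | as diaphoresis |
| palpitations | **no row** | **none seen** |

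- Asked in some form: 9/11 = 82%.
- Not asked: 2/11 = 18%.
- Asked in the endpoint's own terms: 9 − 2 = 7, so 7/11 = 64%, if both the anxiety and the sweating rows count as narrowed. If abnormal sweating is accepted as sweating, it is 8/11 = 73%. The choice is a judgment; the two missing rows are not.
- Dizziness, a Section V example, is also on neither guide. It is not part of outcome j and is not counted above.

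**Step 2. Window.** Rows worded for the first 2 hours: 0 of 9. The Protocol Summary (Foreseeable Risks and Discomforts) puts the stay on the labor and delivery floor at several hours after surgery. The period asked about therefore generally runs past the endpoint's limit. No onset time is recorded, so later symptoms cannot be removed in analysis.

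**Step 3. The second call.** On nominal times the calls are 18 − 4 = 14 to 24 − 2 = 22 hours apart. Both forms stop at transfer. On any of the three stated times for the first call, the second call covers the same early period again, wholly or almost wholly, and no item covers the time after transfer. Measured against Section VII, the second evaluation is missing. Measured against outcome j, which ends at 2 hours, nothing is lost by this.

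**Step 4. Which form is which.** Only one guide title survives extraction, "2-4 HR POSTPARTUM", between the two forms. The Attachments list gives "8.17.2021 18-24 Hour Interview Guide- CLEAN (Instrument/Questionnaire" ahead of the 2-4 hour guide, so the first form is probably the 18-24 hour one. That is an inference. It rests on the list order and on the Summary's statement that the guides share their content. Step 1 holds for both forms whichever is which.

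**Step 5. Other routes for the two symptoms.** Section V makes Epic records a planned source for outcomes, side effects included. The Protocol Summary has the anesthesia and obstetric providers watch for side effects. Section IX has an Adverse Experience Form, and Section VII a review of the 6-week record. None of these puts a blinded, structured question to every patient, as the guides do for the other nine.

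**The case against.** The strongest reply is that little is lost. Epic is a named source and providers monitor for side effects, so a reader who infers that abdominal pain and palpitations could not be recorded at all goes further than the documents allow. That stands: what is missing is collection by the same method as the other nine symptoms. The Methergine label puts palpitation among rarely observed reactions and says abdominal pain occurs occasionally. With about 50 patients per group, comparative information on palpitations would be thin in any case. Abdominal pain soon after a cesarean is also hard to attribute to one drug. Both arms use the same forms, and nothing in the documents shows which arm any bias would favor.

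A reader might also infer that the 18-24 hour form breaks the endpoint, or contradicts the Summary's claim of two timepoints. Neither follows. Outcome j is over by then, and the same Summary sentence calls for identical content, so timepoints may simply mean the occasions of asking. The shortfall is against Section VII alone.

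A third tempting reading is that the SAP's logit GEE for repeated binary measurements would treat two recalls of one period as two times. The SAP does not say which outcomes that model covers, so this remains a possibility.

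Finally, the endpoint list in Section V of the Detailed Protocol places side effects under maternal morbidity, with no symptom list or window. That gives a looser definition, but it does not displace Section II and the Protocol Summary, which agree with each other.

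**Conclusion.** The point holds as a mismatch between endpoint and instrument. Forms followed as written cannot deliver outcome j, because two of its 11 symptoms have no blinded, structured question and the remaining nine are tied to transfer instead of 2 hours, with two of them in narrower wording. The scale is limited: one of the 16 secondary outcomes listed as a to p, with no effect on the primary endpoint.

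The count is certain for the two surviving guides and rests on visible columns only for the data sheet. The statement about the 18-24 hour call depends on one of the two forms being that guide, which is likely but inferred. The correction is worth making because it is cheap and because, without it, the published table would claim more than was asked.

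**What to change.** **If interviews are complete**, as the SAP's past-tense account of excluded patients suggests:
- state that abdominal pain and palpitations were not asked about in the blinded interview, and give any counts separately with their source;
- report the symptom wording and the pre-transfer window as asked, in place of the 2-hour label;
- describe the 18-24 hour interview as repeat recall of the pre-transfer period.

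The cost is a few sentences and table footnotes.

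**If any interviews remain:**
- add abdominal pain and palpitations, and dizziness to match Section V, to both guides and the data sheet;
- use one wording for anxiety and for sweating in the endpoint and the forms;
- have the first guide ask separately about the first 2 hours and about the time from then to the call. With a call at up to 4 hours, as much as 4 − 2 = 2 hours would otherwise go uncovered;
- have the 18-24 hour guide ask about symptoms since the first call, reported apart from outcome j.

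The cost is a minor form amendment within calls already planned. Items added mid-trial will be missing for earlier patients and need their own denominators.

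**In either case**, reconcile the time of the first call across Sections V and VII and the Protocol Summary.

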## **Methergine®**

**(methylergonovine maleate)**

**Tablets, USP**

**(methylergonovine maleate)**

**Injection, USP**

**Rx only**

## **DESCRIPTION**

Methergine® (methylergonovine maleate) is a semisynthetic ergot alkaloid used for the prevention and control of postpartum hemorrhage.

Methergine is available in sterile ampuls of 1 mL, containing 0.2 mg methylergonovine maleate for intramuscular or intravenous injection and in tablets for oral ingestion containing 0.2 mg methylergonovine maleate.

### **Tablets**

Active Ingredient: methylergonovine maleate, USP, 0.2 mg.

Inactive Ingredients: acacia, carnauba wax, D&C Red #7, FD&C Blue #1, gelatin special, lactose, maleic acid, mixed parabens, povidone, sodium benzoate, sodium hydroxide, starch, stearic acid, sucrose, talc, and titanium dioxide.

[figure not shown]
**Ampuls:** 1 mL, clear, colorless solution.

Active Ingredient: methylergonovine maleate, USP, 0.2 mg.

Inactive Ingredients: maleic acid, 0.10 mg; sodium chloride, 7.0 mg; water for injection, qs to 1 mL.

Chemically, methylergonovine maleate is designated as ergoline8carboxamide, 9,10didehydroN[1 (hydroxymethyl)propyl]6methyl, [8ü(S)], (Z)2butenedioate (1:1) (salt).

Its structural formula is

$C_{20}H_{25}N_3O_2 \bullet C_4H_4O_4$  Mol. wt. - 455.51

## CLINICAL PHARMACOLOGY

Methergine (methylergonovine maleate) acts directly on the smooth muscle of the uterus and increases the tone, rate, and amplitude of rhythmic contractions. Thus, it induces a rapid and sustained tetanic uterotonic effect which shortens the third stage of labor and reduces blood loss. The onset of action after I.V. administration is immediate; after I.M. administration, 25 minutes, and after oral administration, 5 to 10 minutes.

Pharmacokinetic studies following an I.V. injection have shown that methylergonovine is rapidly distributed from plasma to peripheral tissues within 23 minutes or less. The bioavailability after oral administration was reported to be about 60% with no accumulation after repeated doses. During delivery, with intramuscular injection, bioavailability increased to 78%. Ergot alkaloids are mostly eliminated by hepatic metabolism and excretion, and the decrease in bioavailability following oral administration is probably a result of firstpass metabolism in the liver.

Bioavailability studies conducted in fasting healthy female volunteers have shown that oral absorption of a 0.2 mg methylergonovine tablet was fairly rapid with a mean peak plasma concentration of  $3243 \pm 1308$  pg/mL observed at  $1.12 \pm 0.82$  hours. For a 0.2 mg intramuscular injection, a mean peak plasma concentration of  $5918 \pm 1952$  pg/mL was observed at  $0.41 \pm 0.21$  hours. The extent of absorption of the tablet, based upon methylergonovine plasma concentrations, was found to be equivalent to that of the I.M. solution given orally, and the extent of oral absorption of the I.M. solution was proportional to the dose following administration of 0.1, 0.2, and 0.4 mg. When given intramuscularly, the extent of absorption of Methergine solution was about 25% greater than the tablet. The volume of distribution ( $Vd_{ss}/F$ ) of methylergonovine was calculated to be  $56.1 \pm 17.0$  liters, and the plasma clearance ( $CL_p/F$ ) was calculated to be  $14.4 \pm 4.5$  liters per hour. The plasma level decline was biphasic with a mean elimination halflife of 3.39 hours (range 1.5 to 12.7 hours). A delayed gastrointestinal absorption ( $T_{max}$  about 3 hours) of Methergine tablet might be observed in postpartum women during continuous treatment with this oxytocic agent.

## INDICATIONS AND USAGE

Following delivery of the placenta, for routine management of uterine atony, hemorrhage and subinvolution of the uterus. For control of uterine hemorrhage in the second stage of labor following delivery of the anterior shoulder.

